**[contact], [contact]**

## **1. Purpose of the Study and Background**

### **1.1 Purpose of the Study:**

The study objective is to determine whether use of Rhopressa accelerates migration of host peripheral corneal endothelial cells to restore the central endothelial cell layer after removal of dysfunctional host endothelium and guttae-covered Descemet membrane from a central 4 to 5-mm diameter area to treat Fuchs endothelial corneal dystrophy (FECD).

### **1.2 Background**

The leading reason for corneal transplantation in the United States is FECD, which is characterized by deposition of abnormal, vision-distorting deposits on Descemet membrane and subsequent apoptosis of corneal endothelial cells resulting in corneal edema. Deposition of guttae begins centrally and progresses peripherally. The current treatment for FECD is endothelial keratoplasty, in which a central 8-mm diameter area of Descemet membrane and dysfunctional endothelium is removed and replaced with healthy donor tissue. This results in rapid visual rehabilitation but requires long-term use of topical corticosteroids to prevent rejection of the donor endothelium. While the chance of rejection of the graft is reduced with Descemet's membrane endothelial keratoplasty (DMEK) relative to other corneal transplants, the risk is still present as is the risk of graft failure, requiring a repeat graft. If a patient's own cells could be used instead of donor tissue, then the need for long-term topical corticosteroids with the secondary risk of steroid-induced glaucoma would be reduced or eliminated.

The peripheral endothelium and Descemet membrane are often relatively healthy in FECD and studies have shown that the peripheral corneal endothelial cells can migrate to cover denuded areas. Therefore, some surgeons have investigated the possibility of removing the central dysfunctional endothelium and most densely guttae-covered area of Descemet membrane in FECD patients without implanting any donor tissue. When a 6-mm diameter area is stripped, the recovery tends to be slow and unreliable. Stripping a smaller area (4-mm diameter) accelerates recovery in many cases, yet some corneas still fail to fully clear within a reasonable time period and delayed clearing can lead to scar formation that degrades vision. A pilot study found that use of ROCK inhibitor eye drops (ripasudil, available outside the USA) resulted in faster and more reliable corneal clearing following Descemet stripping only (DSO) for FECD.

Unpublished data from outside the US indicates that Rhopressa™ may be superior to ripasudil for promoting endothelial cell migration and possible regeneration.

### **1.3 Study Design**

- Prospective, randomized, double-masked, placebo-controlled clinical trial
- Main Outcome Measure: rate of corneal clearing after DSO for FECD

### **2.0 Characteristics of the Research Population**

2.1 **Number of Subjects:** up to 60 FECD patients will be enrolled.

2.2 **Gender of Subjects:** both men and women will be enrolled

2.3 **Age of Subjects:** 18-90 years of age. The rationale for not including minors is that endothelial keratoplasty is performed to treat endothelial dysfunction, a condition usually seen in adults over 40 years of age.

2.4 **Racial and Ethnic Origin:** Subjects may be of any racial or ethnic origin.

2.5 **Inclusion criteria.** The following are requirements for study inclusion:

- At least 18 years of age
- Male or female patient undergoing Descemet stripping only for Fuchs dystrophy.
- Patient is able and willing to administer eye drops.
- Patient is able to comprehend and has signed the Informed Consent form.

**2.6: Exclusion criteria.** Patients with any of the following cannot participate in the study:

- Active intraocular inflammation, corneal ulceration, keratitis, or conjunctivitis.
- Known sensitivity to any of the ingredients in the study medications.
- Abnormal eyelid function.
- History of herpetic keratitis.
- History of non-compliance with using prescribed medication.
- Current or planned pregnancy within the study duration.
- Concurrent involvement or participation in another randomized clinical trial within 30 days prior to enrollment in this study.
- Any ocular or systemic condition (i.e., UNCONTROLLED systemic disease) or situation which in the investigator's opinion may put the patient at significant

risk, confound the study results, or interfere significantly with the patient's participation in the study.

## **2.7 Vulnerable Subjects:**

No potentially vulnerable subjects will be enrolled because there may be no direct benefit to the patient; rather, important knowledge which may benefit future subjects is being sought. As such, the direct benefit would not outweigh risks for vulnerable populations.

Minors will not be enrolled into this study because Fuchs endothelial dystrophy is an adult-onset condition.

Pregnant women will not be enrolled into this study as potential risks and harm to the fetus is unknown.

This study plans to exclude any person who does not speak English as non-English speaking patients are not normally seen at the study site so a translator would not be available to translate the consent form into the patient's native language.

## **3.0 Methods & Procedures**

### **3.1 Study procedures and assessments.**

- Screening and Enrollment: Prospective subjects will be considered for entry into the study. Subjects meeting the inclusion and exclusion criteria will be informed of the opportunity to participate in the study. Subjects will be entered into the study after providing written informed consent. Each subject will be instructed that if they decide not to participate, they may withdraw at any time.
- Randomization: Netarsudil ophthalmic solution 0.02% and placebo eye drops will be dispensed to study subjects in 2.5 ml bottles, identical in appearance. A designated, unmasked, dosing coordinator will apply a coded sticker to each bottle. A computer generated randomization table will be generated. After the study subject signs the informed consent document, the subject will be randomly assigned to receive netarsudil or placebo (netarsudil vehicle). Both the subject and the investigator will remain masked as to the assigned treatment. If a study participant elects to have both eyes enrolled in the study, the dosing coordinator will automatically assign the second eye to the opposite treatment group from that of the first eye.
- Study Treatment Regimen: Subjects will be instructed to instill the assigned eye drop into the study eye once nightly for the 3-month study duration or until 2 weeks after corneal clearing is complete, whichever occurs sooner.

- Study Drug Accountability: Subjects will be asked to bring back to the clinic all study bottles, both used and un-used. All study drug bottles will be reconciled and recorded.
- Rescue Medication: If corneal clearing is not complete or seems to have stalled at the 5-week exam, the investigator can ask the dosing study coordinator to reveal the randomization assignment. If the eye was randomized to placebo it can be treated once daily (at night) with netarsudil (open label) for 7 weeks, whereas if the eye was originally randomized to netarsudil, it can be treated twice daily with netarsudil (open label) for 7 weeks or until complete clearing, whichever is sooner, in lieu of using the masked study drop.
- Examinations:
  - Schedule: Study visits include screening, as well as 1 day, 1 week, 3 weeks, 5 weeks, 7 weeks, 9 weeks and 12 weeks after DSO (Table 1). If complete healing is noted at the 3-, 5- or 7-week exam, the next following exam can be omitted.
  - Procedures: Medical and ophthalmic histories will be updated, adverse events will be recorded, and visual acuity will be assessed at each visit. A slit lamp examination will be performed at each visit to assess corneal clearing and to document any conjunctival or lid hyperemia, stromal inflammation, superficial punctate keratitis, other surface toxicity of the cornea, neovascularization of the cornea, and cells or flare in the anterior chamber. Subjects will also complete a 15-question visual disability questionnaire validated for use with FECD. Manifest refraction, intraocular pressure, ultrasonic pachymetry, and corneal imaging with anterior segment optical coherence tomography will be performed at selected exams as indicated in the Table. Corneal endothelial cell density will be measured by specular microscopy if possible at the 9- and 12-week exams. Any routine exam procedures that were already performed within 90 days of study enrollment do not have to be repeated at the screening exam.
  - Records release: Subjects may be asked to sign a records release form in case the subject sees another eye specialist while enrolled in the study.
  - Unscheduled examinations: Subjects will be instructed to return for extra examinations if they note any problems with the eye.
  - Study completion: Subjects will be considered to have completed the study after they complete the 12-week examination.

- Subject withdrawal or discontinuation: Each subject may voluntarily discontinue the study at any time they choose. Subjects who cannot complete the study for administrative reasons (e.g., non-compliance, failure to meet visit schedule, etc.) will be discontinued from the study. Discontinued subjects may be replaced. For subjects withdrawn from the study, the same measurements and assessments should be performed as done at the 3-month exit exam. Adverse events should be followed up until resolution or stabilization of the adverse event.

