Anticipated adverse events in subjects who had cataract surgery combined with DSO include cystoid macular edema and capsular haze. Cataract formation or progression is an anticipated adverse event in any eye that was phakic and underwent DSO without combined cataract surgery. These anticipated surgical adverse events will be recorded on the electronic case report form (eCRF) for each exam rather than on separate adverse event forms.

The most common anticipated adverse events associated with use of Rhopressa™ include: eye discomfort, irritation, itching or pain, foreign body sensation, increased tearing, blurry vision, conjunctival hyperemia, conjunctival hemorrhage, eyelid swelling, and verticillata. Additional adverse events reported with use of Rhopressa™ include: reduced visual acuity, allergic conjunctivitis, dry eye, keratitis, conjunctival swelling, photophobia, and corneal staining.

Adverse events: The type, severity, duration and frequency of the following anticipated adverse experiences and any other unanticipated ocular adverse events will be tabulated. If a patient experiences an adverse reaction, appropriate medical treatment will be provided. Examples may include:

- Intraocular pressure elevation which requires intervention
- Development of capsular haze which requires intervention
- Cystoid macular edema
- Iritis

Anticipated rare adverse events include retinal detachment, iris synechiae/atrophy, epiretinal membrane, infectious keratitis or conjunctivitis, branch retinal vein occlusion, or endophthalmitis.

Serious Adverse Event: A serious adverse event is one that results in any of the following outcomes: death, a life-threatening adverse event, inpatient hospitalization or prolongation of existing hospitalization, a persistent or significant disability/ incapacity, or a congenital anomaly/birth defect. In the event of a serious adverse event, the investigator will maintain complete documentation and promptly inform the study drug manufacturer and the governing Institutional Review Board (IRB) of the serious adverse event within their required reporting period.

Fellow eye: Patients in this population tend to be affected with the eye condition bilaterally, so many of the study subjects may undergo surgery on the fellow eye during study participation. Routine fellow-eye post-surgical complications will not be transcribed to the eCRF unless the fellow eye is enrolled in the study at the time of the event.

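### Nothing bars a second eye from entering after the first eye's code is broken, and for such an eye the arm is known before it is enrolled

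*Combined protocol and SAP*

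**What the plan says.** Four statements in the combined protocol and SAP bear on this.

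- **Entry of a second eye (3.1, Randomization).** It is optional: "If a study participant elects to have both eyes enrolled in the study". No deadline is given, and nothing asks for both eyes to be declared before the first is randomized.
- **Its arm (3.1, Randomization).** It follows from the first eye's arm: "the dosing coordinator will automatically assign the second eye to the opposite treatment group from that of the first eye".
- **Disclosure of the first eye's arm (3.1, Rescue Medication).** The trigger is "If corneal clearing is not complete or seems to have stalled at the 5-week exam"; then "the investigator can ask the dosing study coordinator to reveal the randomization assignment". The open-label treatment that may follow depends on the original arm, so it can also disclose that arm to the subject.
- **Timing of fellow-eye surgery (4.1, Fellow eye).** The plan expects that "many of the study subjects may undergo surgery on the fellow eye during study participation". Fellow-eye complications are not transcribed "unless the fellow eye is enrolled in the study at the time of the event", so the plan foresees fellow eyes in the trial, possibly from different dates.

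On the other side, 3.1 says in general terms: "Both the subject and the investigator will remain masked as to the assigned treatment". Section 3.2 counts subjects, analyses all who were randomized, and does not mention second eyes.

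**The concern.** Concealment means that nobody deciding on entry knows which arm the unit will receive. An opposite-arm rule preserves it while the first eye's arm is unknown. Once that arm is revealed, the second eye's arm is certain: netarsudil if the first eye had placebo, placebo if it had netarsudil. A subject whose first eye was slow on placebo then has a reason to join, and one whose first eye was slow on netarsudil has a reason to decline.

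If that happened, netarsudil second eyes would come disproportionately from slow healers. An unpaired comparison of eyes would then be biased against the drug. A within-pair comparison would be biased toward it by regression to the mean, because pairs would be kept when the placebo eye did badly and lost when the netarsudil eye did. Pairing handles correlation between eyes but not selective entry.

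**Working it through.** **1. The plan's own figure.** Section 3.2 gives means 0.6 and 0.8, SD 0.30, one-sided 5%, 80% power, 29 per arm. The noncentral t calculation gives power 0.793 at 28 per arm and 0.806 at 29, so 29 reproduces. Allowing 3% dropout, 58/0.97 = 59.8, or 60. The sample size is not in dispute.

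**2. When concealment is lost.**

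| Second eye enters | First eye's arm | Second eye's arm before entry |
|---|---|---|
| Declared before the first eye is randomized | Not yet drawn | Concealed |
| Later, no reveal | Masked; interim outcome may be known | Concealed, though it may be guessed |
| After a reveal | Known | Known |

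Only the third row loses concealment, and no text excludes it.

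**3. How many first eyes could be unmasked.** Assume the planning moments, given for 4 and 6 weeks, also hold at the 5-week exam. For any distribution with mean m and SD s, Cantelli's inequality gives P(not fully clear) ≥ 1 − s²/[s² + (1 − m)²].

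- Placebo: 1 − 0.09/(0.09 + 0.16) = 0.64
- Netarsudil: 1 − 0.09/(0.09 + 0.04) = 0.31
- Equal arms: (0.64 + 0.31)/2 ≈ 0.47

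A normal model gives 0.91 and 0.75, average 0.83. These are shares eligible for a reveal, not shares revealed.

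**4. Size of the bias, by simulation.** Inputs from the plan: 60 first eyes split 30:30, means 0.6 and 0.8 (or 0.6 and 0.6 for no effect), SD 0.30. Assumptions not in the documents: beta-distributed outcomes; inter-eye correlation 0.3–0.8; 60% or 100% of subjects with a second eye available; a first eye below 95% clear counts as eligible for a reveal; after a reveal, 90% join if the second eye would get netarsudil and 10% if placebo; without a reveal, 50% join. "Late" means after the first eye's 5-week exam.

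| Scenario | Second eyes with known arm | Unpaired estimate (true 0.20) | Within-pair estimate (true 0.20) | Paired one-sided rejection, no effect |
|---|---|---|---|---|
| Half late, half of eligible eyes unmasked | about 20% | about 0.19–0.20 | about 0.20–0.21 | about 5%, no clear inflation |
| All late, all eligible eyes unmasked | about 70% | 0.16–0.19 | 0.21–0.24 | about 6–11% |

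With all late and all unmasked but 70%/30% joining, the estimates are about 0.18–0.20 unpaired and 0.20–0.22 within pairs. With no selection by arm, both stay at 0.20 and rejection stays near 5%. The ranges cover several runs of 800 to 3,000 trials per setting, so the last digit carries simulation error.

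**The case against.** A reader might infer that second eyes as a class are enrolled without concealment, and that most enter with their arm known. The documents do not support this. The reveal is something the investigator may request, with no expected rate. Fellow-eye surgery may fall anywhere in a 12-week participation, so entry before week 5 fits the text equally well. The 70% share appears only when every second eye is late and every eligible first eye is unmasked. Table 1 lists consent and assignment once, at screening, so the sponsor may intend both eyes to be declared then.

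A reader might also infer that the trial is tilted toward a false positive. That does not follow either. Nothing shows that selection will occur. The unpaired bias runs against the drug, so it would not produce a false positive in the planned one-sided test. And 3.2 analyses randomized subjects: if that means first eyes only, this bias is zero.

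These points limit the size and certainty of the problem, but the gap remains. The general masking statement cannot hold after a permitted reveal, no rule stops a second eye entering at that stage, and the plan does not say whether second eyes count in the primary analysis.

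**Conclusion.** The point holds for one group: second eyes that enter after their fellow's code is broken. For them the arm is known in advance and entry can be selected by arm. The plan's rules, followed as written, allow this. The figure of at least about 47% of first eyes eligible for a reveal rests on the planning moments holding at week 5. The size of the bias is unknown. It ranges from about 0.01 or less on the proportion scale to, under deliberately extreme assumptions, a shift of up to about 0.04 (0.20 to 0.16 unpaired, or 0.20 to 0.24 within pairs), with paired type I error of about 6–11% against a nominal 5%. The closing step costs little, so this is a cheap improvement and does not make the design unsound.

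**What to change.** In 3.1 (Randomization), state that a subject may contribute two eyes only if both are declared at consent, before the first eye is randomized, with one random draw deciding which eye receives netarsudil. A second eye not declared then is not enrolled. At minimum it is left out of the primary analysis, which 3.2 should define as first (randomized) eyes plus pre-declared pairs. Record the date of each second-eye decision.

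A cut-off at the first eye's 5-week exam or code break would be weaker, because it still admits second eyes after the 3-week result has been seen.

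The cost is a few sentences in 3.1 and 3.2 and the loss of a few late second eyes. Enrolment of 60 is counted in subjects, so the target is unaffected, and no treatment or rescue rule has to change.

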**Table 1.**

	Screening Randomization	1 day after DSO	7 ± 2 days after DSO	3 ± 1 weeks after DSO	5 ± 1 weeks after DSO	7 ± 1 weeks after DSO	9 ± 1 weeks after DSO	Exit visit 12 ± 2 wks after DSO
Informed Consent	X							
Inclusion/Exclusion Criteria	X							
Medical and ophthalmic history	X	X	X	X	X	X	X	X
Adverse Events	X	X	X	X	X	X	X	X
Uncorrected visual acuity (Snellen)	X	X	X	X	X	X	X	X
Visual disability questionnaire	X			X	X	X	X	X
Assignment to netarsudil or placebo	X							
Manifest refraction and corrected distance vision (Snellen) if possible	X			X	X	X	X	X
Slit lamp exam	X	X	X	X	X	X	X	X
Endothelial cell density (if possible)							X	X
Intraocular pressure	X				X	X	X	X
Ultrasonic pachymetry	X				X	X	X	X
Anterior segment optical coherence tomography	X			X	X	X	X	X

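### The week-5 rescue rule in 3.1 reveals the arm to set a dose that could be dispensed masked, and the reveal also discloses an opposite-arm fellow eye

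*Combined protocol and SAP*

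**What the plan says.** - **Masking.** Section 1.3 describes a double-masked trial, and 3.1 states: "Both the subject and the investigator will remain masked as to the assigned treatment".
- **Rescue.** Section 3.1 (Rescue Medication) makes an exception at the 5-week exam for incomplete or apparently stalled clearing: "the investigator can ask the dosing study coordinator to reveal the randomization assignment". A placebo eye can then receive open-label netarsudil once nightly for 7 weeks. For a netarsudil eye, "it can be treated twice daily with netarsudil (open label) for 7 weeks or until complete clearing, whichever is sooner". No other use of the reveal is given. Section 1.2 supplies a clinical reason for rescue: "delayed clearing can lead to scar formation that degrades vision".
- **Dispensing.** Section 3.1 (Randomization) has drug and vehicle in bottles that look the same. It adds: "A designated, unmasked, dosing coordinator will apply a coded sticker to each bottle".
- **Second eye.** If both eyes are enrolled, "the dosing coordinator will automatically assign the second eye to the opposite treatment group from that of the first eye". Section 4.1 (Fellow eye) expects that many subjects may have fellow-eye surgery while in the study.
- **Assessment.** "A slit lamp examination will be performed at each visit to assess corneal clearing", but no grader is named. Section 3.2 sets the primary endpoint at 4 and 6 weeks and also refers to a 4-week primary endpoint. Table 1 has no visit at either time. The nearest are 3 ± 1, "5 ± 1 weeks after DSO" and 7 ± 1.

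**The concern.** The investigator has to know only that an eye needs rescue. The dose that follows is fixed by the arm, and someone who already knows the arm can dispense it. The exception therefore gives up masking for a purpose that does not require it.

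Two kinds of data are exposed.

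1. **The fellow eye.** Assignment of the second eye is deterministic, so learning one arm means learning both. The second eye need not be rescued for this to happen. If its surgery comes later, the reveal can precede its primary readings. If it comes much later, the arm can be known before the eye is enrolled, and its allocation is then no longer concealed.
2. **The rescued eye.** Slit-lamp clearing, hyperemia, acuity, questionnaire and adverse-event data after the reveal are open-label. Section 3.2 names no analysis of these beyond the primary, so most of them are descriptive. The primary is reached by one route only, a 6-week value read at the 7 ± 1 week visit.

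**Working it through.** **Plan's own figure.** Section 3.2 gives 29 per arm for means 0.6 and 0.8, SD 0.30, one-sided 5%, 80% power. The normal approximation is 2 × (1.645 + 0.842)² × 0.30² / 0.20² = 27.8, so 28. The two-sample t-test needs 29 (power 0.806 at 29, 0.793 at 28). With 3% drop-out, 58 / 0.97 = 59.8, so 60. The figure reproduces, and masked rescue changes none of its inputs.

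**Can the same doses be given masked?** Give every rescued eye two coded bottles.

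| Original arm | Night bottle | Morning bottle | Active drops per day |
|---|---|---|---|
| Placebo | netarsudil | vehicle | 1 |
| Netarsudil | netarsudil | netarsudil | 2 |

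These are the plan's two doses, started at the same visit.

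**How many eyes would be eligible for a reveal?** Assumptions: clearing lies between 0 and 1, the 3.2 planning values hold at week 5, and each arm has 29 eyes. Let D = 1 − clearing. For any distribution, P(D > 0) ≥ E[D]² / E[D²], where E[D²] = mean² + SD².

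- Placebo: 0.4² / (0.4² + 0.3²) = 0.16 / 0.25 = 0.640; × 29 = 18.6 eyes.
- Netarsudil: 0.2² / (0.2² + 0.3²) = 0.04 / 0.13 = 0.308; × 29 = 8.9 eyes.
- Total: 27.5 / 58 = 47%, as a lower bound.

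Fitted distributions give more, depending on what counts as complete. Beta distributions matched to mean and SD have parameters (1.00, 0.667) for placebo and (0.622, 0.156) for netarsudil.

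| Cut-off for complete | Placebo | Netarsudil | Eyes of 58 |
|---|---|---|---|
| 0.90 | 0.785 | 0.377 | 33.7 (58%) |
| 0.95 | 0.864 | 0.442 | 37.9 (65%) |
| 0.99 | 0.954 | 0.566 | 44.1 (76%) |

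A normal distribution clipped to 0–1 gives 0.856 and 0.456, or 38.0 eyes (66%).

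For two-eye subjects with first eyes allocated 1:1, at least 10 × (0.640 + 0.308) / 2 = 4.7 first eyes per 10 subjects are eligible on average (5.8 to 7.6 over the beta cut-offs).

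**When does a first-eye reveal reach the second eye?** Let the second surgery follow the first by d weeks. A reveal at first-eye week 5 falls at second-eye week 5 − d.

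| Reveal precedes the second eye's | Nominal visits | Least favourable windows (reveal at week 6, second-eye exam at its earliest) |
|---|---|---|
| 3-week exam | d > 2 | d > 4 |
| 5-week exam | d > 0 | d > 2 |
| 7-week exam | any d ≥ 0 | d > 0 |
| surgery | d > 5 | d > 6 |

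The 4-week value can come from the 3 ± 1 or 5 ± 1 visit, and the 6-week value from the 5 ± 1 or 7 ± 1 visit. So beyond a 2-week gap (4 in the worst case) both primary readings follow the reveal, whichever visits supply them. With the reveal at the early edge of its window (week 4), it precedes surgery once d > 4, so that threshold runs from 4 to 6 weeks.

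**The case against.** The exception is disclosed, optional and clinically motivated. The fellow-eye harm needs several things together: both eyes enrolled, a later second surgery, a first eye not clear at week 5, an investigator who uses the option, and that investigator grading the second eye. The plan gives no frequency for any of these. All of this stands, and it limits how strongly the point can be put.

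A reader might infer more than the documents support:

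- *That an unmasked investigator grades the primary.* Section 3.1 names no grader. It also names no separate masked one, so the risk is open but not established.
- *That about half the eyes will be unmasked, or that type I error is inflated.* The 47% is eligibility. Uptake could be anywhere from none to all of those eyes. An inflated error rate would need an assumed share unmasked and an assumed grading shift, and the plan gives neither.
- *That the rescued eye's primary is generally compromised.* The reveal follows the 5-week exam, whose window extends to week 6. A 4-week value, or a 6-week value read at that exam, precedes the reveal.
- *That masked rescue restores the drug–placebo comparison.* A rescued placebo eye receives netarsudil either way. Where the 6-week value is read afterwards, that crossover is the larger problem and masking leaves it untouched.

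An independent masked grader is a fair alternative for the slit-lamp readings and leaves rescue care as it is. It would not conceal the second eye's arm before enrolment. It is also fair that a stalled cornea may raise the question of keratoplasty (4.3 names DMEK and DSEK), so a loosely worded surgical exception could reopen many of the same reveals. The fix has to be worded to prevent that.

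**Conclusion.** The point holds as an inexpensive improvement to the design. It does not show that the result would be biased. The reveal serves only to pick one of two fixed doses, and 3.1 already has the staff and bottles to give them masked. Its reach extends to any second enrolled eye, whose primary readings can both fall after the reveal once the surgeries are more than 2 weeks apart (4 with the least favourable windows).

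On the planning values the trigger would not be rare: at least about 47% of eyes, if those values apply at week 5, clearing is bounded by 0 and 1, and the 29 per arm are read as eyes. The number of two-eye subjects, the gap between surgeries, the uptake of reveals and the size of any bias remain unknown.

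**What to change.** In 3.1 (Rescue Medication):

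- Let the investigator request rescue without being told the arm. The unmasked coordinator dispenses a coded night bottle (netarsudil for all) and a coded morning bottle (vehicle for ex-placebo eyes, netarsudil for ex-netarsudil eyes).
- Allow a code break only where a safety or surgical decision cannot be made without the arm, and log the date and reason. State that incomplete clearing alone is not a ground.
- State one stopping rule for both arms, such as 7 weeks or complete clearing, whichever is sooner. The current sentence can be read as applying the clearing limit only to the twice-daily dose. This is a wording query, but different rules by arm could also disclose the arm.

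**Cost.** Protocol wording, extra coded bottles (with more to keep apart in two-eye subjects), some coordinator work, and one added vehicle drop a day for up to 7 weeks in rescued ex-placebo eyes. The investigator would not know whether the eye had already been on active drug. Hyperemia may still hint at the arm. Sample size is unchanged. How the analysis treats rescued eyes needs its own rule, which this change does not supply.
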